# **5 TREATMENT OF PATIENTS**

# 5.1 **Presentation of Study Treatments**

# 5.1.1 KY1044

KY1044 is presented as a clear to opalescent sterile solution that is colorless to slightly yellow, brown or brown-yellow, and is filled to a nominal 1 mL volume in a single-dose 2 mL clear glass vial. KY1044 is formulated at a nominal concentration of 50 mg/mL in 25 mM L-histidine/histidine hydrochloride, 240 mM sucrose and 0.02% (weight/volume) polysorbate 80 at pH 5.5. KY1044 will be diluted in 0.9% NaCl solution prior to administration via IV infusion.

# 5.1.2 Atezolizumab (TECENTRIQ®)

Atezolizumab is presented as a colorless to slightly yellow sterile solution, filled to a nominal 20 mL volume in a single-dose vial. Atezolizumab is formulated at a nominal concentration of 60 mg/mL in glacial acetic acid (16.5 mg), L-histidine (62 mg), sucrose (821.6 mg) and polysorbate 20 (8 mg) at a pH of 5.8. Atezolizumab will be added to an IV infusion bag containing 0.9% NaCl solution prior to administration.

# 5.2 Study Treatment Administration

The study treatment is defined as KY1044 as single agent or in combination with atezolizumab. All dosages prescribed and dispensed to patients and all dose changes during the study must be recorded in the patient's hospital files and on the electronic case report form (eCRF).

# 5.2.1 Dosing Regimen

Study treatments	Pharmaceutical form	Route of administration	Dose			Frequency and/or Regimen
			Phase 1	Phase 2 dose assessment	Phase 2	
KY1044	Solution	IV infusion	Escalating doses starting at 0.8 mg	One of two biologically relevant doses	RP2D	Q3W (±3 days)
Atezolizumab	Solution	IV infusion	1200 mg	1200 mg	1200 mg	Q3W (±3 days)

Table 5-1:Dose and Treatment Schedule

Q3W=every three weeks

Patients are to receive KY1044 doses (either as single agent or in combination with atezolizumab) within a 3 days visit window. However, the next dose (as single agent or in combination) may be delayed by up to 7 days to recover from previous Aes.

If doses are not received within this time frame, the dose should be missed and patients should receive the next planned dose according to the schedule on Day 1 of the next cycle. If the patient experiences a related toxicity, the management guidelines provided in Section 5.6 should be followed.

# 5.2.2 Infusion of IMPs

KY1044 will be administered via IV infusion over 30 to 60 minutes. If well tolerated at the first infusion, subsequent infusions may be given over 30 minutes.

Atezolizumab will be administered via IV infusion over 60 minutes. If well tolerated at the first infusion, subsequent infusions may be given over 30 minutes.

When given in combination, both IMPs are to be administered within 24 hours, however separate infusion sets must be used for each investigational product. KY1044 is to be administered first and promptly followed by a saline solution flush to empty the line as

described in the pharmacy manual. Slow saline infusion will continue for approximately 1 hour before starting the atezolizumab infusion in the same infusion site. There should be a period of at least 1 hour after the infusion(s) are complete whereby the patient requires close observation.

After receiving the first infusion in Phase 1, patients will be either hospitalized or remain in the clinic for at least 6 to 8 hours until the last assessments. They will be provided with instructions for after hour care per institutional standard and will return to the clinic on C1D2. At all other infusion visits the observation period after the infusion should be at least 3 hours before patients are discharged. In Phase 2, the observation period after infusion of IMP should initially be at least 3 hours before patients are discharged. This time window maybe further reduced during later cycles and when more safety data for each patient are available.

Neither KY1044 or atezolizumab should be co-administered with other drugs through the same IV line. The date, start time, completion time and time and length of any interruptions must be recorded in the eCRF.

Further instructions for the preparation and administration of KY1044 and atezolizumab are described in the Pharmacy Manuals.

# 5.2.3 Precautions for IMP Administration (KY1044 and Atezolizumab)

A physician must be present at the site or immediately available to respond to emergencies during all administrations of KY1044 alone or with atezolizumab. Fully functional resuscitation facilities should be available. KY1044 or atezolizumab must not be administered via IV push or bolus.

In each cohort of the dose escalation of KY1044 as a single agent, dosing will be staggered such that administration of the first patient in each cohort is separated by at least 48 hours from dosing the next patient. Subsequent patients will be treated at least 24 hours apart during the Phase 1 dose escalation part of the study.

In the combination cohorts, dosing will be staggered, such that administration of the first patient in the first cohort is separated by at least 72 hours from dosing the next patient, with subsequent patients being treated at least 24 hours apart in this cohort. In subsequent cohorts the first patient in each cohort will always be dosed 48 hours apart from the next patient. Subsequent patients will be treated at least 24 hours apart during the dose escalation part of the study.

# 5.2.4 Monitoring of IMP Administration (KY1044 and Atezolizumab)

Patients will be monitored during and after the infusion with assessment of vital signs at the times specified in Section 6.5.7.

In the event of an infusion-related reaction  $\leq$ Grade 2, the infusion rate of KY1044 or atezolizumab must be decreased by 50% or interrupted until resolution of the event (up to 4 hours) and re-initiated at 50% of the initial rate until completion of the infusion. If the infusion reaction is caused by KY1044, the atezolizumab infusion may be delayed until the next day and/or until recovery from the event. For these patients, subsequent infusions may be administered at 50% of the initial rate and premedication should be considered. In the event of more severe infusion reactions (CTCAE v5 >Grade 2), IMP should be permanently discontinued.

# 5.2.5 Ancillary Treatments

Patients should not receive premedication to prevent infusion reaction before the first infusion of KY1044, in order to determine if premedication is necessary. If a patient experiences an infusion reaction, he/she may receive premedication on subsequent dosing days. The premedication should be chosen per institutional standard of care, at the discretion of the treating physician.

Acute allergic reactions should be treated as needed per institutional standard of care. In the event of anaphylactic/anaphylactoid reactions, this includes any therapy necessary to restore normal cardiopulmonary status. If a patient experiences a Grade 3 anaphylactic/anaphylactoid reaction, the patient will be discontinued from the study.

Guidelines on management of KY1044 and atezolizumab infusion reactions are provided in Table 5-5.

The CTCAE v5 category of "Infusion related reaction" should be used to describe KY1044 and atezolizumab infusion reactions, unless the Investigator considers another category, such as "Allergic reaction," "Anaphylaxis," or "Cytokine release syndrome" more appropriate in a specific situation.

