# 3.2 Study Flow

Patients will undergo assessments during a (maximum) 28-day screening period, pre-dose and periodically during treatment, as outlined in Section 6. For both regimens of KY1044 administration as single agent and in combination with atezolizumab, treatment will continue until a patient experiences unacceptable toxicity, progressive disease as per iRECIST and/or withdrawal of consent.

Safety follow-up will be performed 90 days after the end of treatment.

Patients who do **not** have progressive disease (as per RECIST 1.1/iRECIST) at the time of discontinuing treatment will receive tumor assessments for evaluation of PFS until disease progression, or starting alternative treatment or the overall end of study (EOS) if earlier (see Section 8.2.1).

All patients who do not withdraw consent for the study will be followed up for survival unless they are lost to follow-up, or overall EOS has been declared (see Section 3.6).

Figure 3-2: Study Flow per Patient

\* Note: Additional provisions may be made for patients who are ongoing on treatment and are still receiving clinical benefit at 48 months for continuation of treatment.

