# 5.6 Dose Modifications and Management of Toxicities

#### 5.6.1 Dose Modifications and Dose Delays

For patients who do not tolerate the protocol -specified dosing schedule, dose adjustments are permitted to allow the patient to continue the study treatment. The following guidelines must be followed:

- If a patient experiences an AE meeting the criteria for a DLT as outlined in Section 5.5 (including events occurring after Cycle 1), treatment should be withheld. Dose modifications for toxicities related to the study medication are summarized in Table 5-5. Following resolution of the toxicity to Grade 1 or to the patient's baseline value (as outlined in the safety management guidelines in Table 5-5), the patient may resume study treatment at the same or the next lower dose level (Table 5-2, Table 5-3) assessed to be safe (on the same dosing schedule [administration every 21 days]), if there is no evidence of disease progression as per iRECIST.
- For patients in the dose escalation part of the study receiving KY1044 in combination with atezolizumab, the KY1044 dose level will be lowered to the next lower dose level. **Dose reductions of atezolizumab are not allowed.**
- The decision to resume treatment with KY1044 as single agent or in combination with atezolizumab following the occurrence of a DLT is at the discretion of the Investigator. If the Investigator considers it to be in the patient's best interest to resume therapy before the toxicity has resolved to Grade 1, or to resume without dose reduction, this may be permitted on a case by case basis, following discussion with the Medical Monitor.
- Dose reductions for KY1044 to below 0.24 mg (less than starting dose -1) are not permitted.
- If a patient who misses more than one consecutive dose due to study treatment -related toxicity experiences clinical benefit, and in the opinion of the Investigator it is in the patient's best interest to remain on study, then the patient may continue treatment after discussion with the Medical Monitor.

- Patients who discontinue study treatment for a study related AE or a study -related abnormal laboratory value must complete their EOT visit and safety followup procedures as described in Section 5.6.2 below and be followed up for PFS and survival (please refer to Section 8.2.2).

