# Table 5-5: Management of Toxicities Defined as Study Treatment-related Only

Infusion Reaction and Cytokine Release Syndrome (CRS)					
Grade	CTCAE description	Management	Specialist referral		
2	Mild transient reaction; infusion interruption not indicated; intervention not indicated Therapy or infusion interruption indicated but responds promptly to symptomatic treatment (eg, antihistamines, NSAIDS, narcotics, IV fluids); prophylactic medications indicated for ≤24 hours	
 
Drug infusion rate may be decreased, or infusion temporarily interrupted, until resolution of the event
 
Consider reducing the rate of infusion upon re-initiation or subsequent infusions
 
NSAIDs (eg, acetaminophen), antihistamines, opioids, and corticosteroids may be used per Investigator/ institutional guidelines
 
Consider premedication for subsequent infusions per Investigator/ institutional guidelines
 
If CRS is suspected (very high fever and precipitous drops in blood pressure, myalgia, change in mental status) treat with corticosteroids according to local standards (and/or with tocilizumab)
 
Take blood for cytokine measurements immediately after the occurrence of the AE and during treatment
 
			
3	Prolonged (eg, not rapidly responsive to symptomatic medication and/or brief interruption of infusion); recurrence of symptoms following initial improvement; hospitalization indicated for clinical sequelae	
 
Permanently discontinue ICI
 
For severe/life-threatening reactions, manage the patient as clinically appropriate (eg, antihistamines, oxygen, fluids, opioids, corticosteroids, bronchodilators, etc.) per Investigator/institutional guidelines
 
Provide supplemental oxygen, fluids, and other resuscitative measures and/or measures for symptomatic relief (see under Grade 2, above) as needed. Monitor vital signs (eg, BP, HR, respiration, and temperature) every 15 ±5 minutes until resolution
 
	✓ Refer to allergist to prevent future reactions		
4	Life-threatening consequences; urgent intervention indicated				

Amended Clinical Trial Protocol 07 KY1044/SAR445256-KY1044-CT01/TCD17370 - alomfilimab 10-Nov-2021 Version number: 1

HAEMATOLOGICAL					
Grade	CTCAE description	Management	Specialist referral		
Anemia	Anemia				

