### 8 WITHDRAWAL OF PATIENTS FROM TREATMENT AND/OR THE STUDY

Patients are free to withdraw from participation in the study at any time, without prejudice to their further care. In some circumstances, patients may be discontinued from study treatment but continue certain study assessments, as described in Section 8.1.

The Investigator should discontinue study treatment for a given patient if, on balance, he/she believes that continuation would be detrimental to the patient's well-being.

Study treatment may be discontinued and/or patients may be withdrawn from the study under the following circumstances:

- 1. Withdrawal of consent (see Section 8.1.1)
- 2. Severe non-compliance with the protocol as judged by the Investigator
- 3. Patients incorrectly initiated on study treatment (eg, patient has been determined to have met one or more of the exclusion criteria for study participation at study entry and continuing study treatment might constitute a safety risk).

- 4. AEs that, in the opinion of the Investigator or the Medical Monitor, contraindicate further dosing. (Patients on combination therapy who need to discontinue KY1044 due to AEs, also need to discontinue atezolizumab. In the case that a patient needs to discontinue atezolizumab due to acute infusion reactions or ADAs, KY1044 may be continued after discussion with the Medical Monitor)
- 5. Pregnancy
- 6. Disease progression, (unless, in the opinion of the Investigator, the patient is still receiving clinical benefit, whereby the patient will be treated until the confirmatory progressive disease per iRECIST (Note: patients with rapid tumor progression or with symptomatic progression that requires urgent medical intervention will not be eligible to continue to receive treatment)
- 7. Study terminated by the Sponsor (see Section 3.7)
- 8. 48 months of treatment
- 9. Lost to follow-up

Regardless of the reason for discontinuation, if possible, all patients should undergo End of Treatment procedures and enter the 90 days safety follow-up period. After the safety follow-up period, patients will have their End of Study visit (Section 8.2). All data available for the patient at the time of withdrawal and all reasons for withdrawal, must be recorded in the eCRF.

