# 8.1 Follow-up of Patients Off Treatment

If a patient needs to withdraw from study treatment for AEs or other safety reasons (reasons 3 and 4 above), but does not have disease progression, they will continue with tumor progression assessments in accordance with the study schedule until they progress as per iRECIST or until they start another anti-cancer therapy or when the overall end of the study is reached. Patients who withdraw consent to treatment but who accept continued monitoring (see Section 6.2.1) will also continue in the same way. Continuation of patients who stop treatment for reasons of non-compliance should be discussed between the Investigator and the Medical Monitor.

All patients (all reasons 1 to 6 listed above) will be followed up at 3 monthly intervals (telephone followup is acceptable) to obtain survival information after the start of treatment. These data will be recorded in eCRF.

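### Protocol 5.2.5 removes a patient with Grade 3 anaphylaxis from the study, while the follow-up rules keep that patient on tumor scans and survival contact

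*Protocol*

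**What the plan says.** Section 5.2.5 (Ancillary Treatments) gives an instruction for one event: "If a patient experiences a Grade 3 anaphylactic/anaphylactoid reaction, the patient will be discontinued from the study".

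Elsewhere the protocol separates stopping treatment from leaving the study. Section 8 notes that in some circumstances "patients may be discontinued from study treatment but continue certain study assessments, as described in Section 8.1". The follow-up rules are then:

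- **Section 8.1**, on patients who stop for adverse events or other safety reasons without progression: "they will continue with tumor progression assessments in accordance with the study schedule". Survival contact every 3 months covers discontinuation reasons 1 to 6, and adverse events are reason 4.
- **Section 5.6.1**: patients who stop for a study-related adverse event must complete the end-of-treatment and safety follow-up procedures and "be followed up for PFS and survival (please refer to Section 8.2.2").
- **Section 3.2**: patients without progression "at the time of discontinuing treatment will receive tumor assessments for evaluation of PFS until disease progression". It adds: "All patients who do not withdraw consent for the study will be followed up for survival", with exceptions only for loss to follow-up and the overall end of study.
- **Section 8.2.2** repeats both duties.

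For the nearest related events, Section 5.2.4 says: "In the event of more severe infusion reactions (CTCAE v5 >Grade 2), IMP should be permanently discontinued". Table 5-5, for Grade 3 and 4 infusion reactions, says: "Permanently discontinue ICI". Neither mentions whether the patient stays in the study.

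**The concern.** Section 5.2.5 is mandatory and specific to the event, and it names the study rather than the treatment. None of the four follow-up sections makes an exception for anaphylaxis. A site that lets the specific instruction override the general ones would stop scans and survival contact for a patient whom the rest of the protocol keeps under observation.

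The reason for stopping would be toxicity. PFS, DOR and OS would then be censored for a cause that may be related to outcome, which Kaplan-Meier estimation assumes is not the case.

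**Working it through.** There is no figure in the plan to reproduce. The check compares the sections and then works out what a literal reading would do to one patient's data.

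**1. Is there a conflict?** Anaphylaxis is an adverse event, so it falls under Section 8 reason 4.

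| Question | Section 5.2.5, literally | Sections 8.1, 5.6.1, 3.2, 8.2.2 |
|---|---|---|
| Scans after the stop, no progression | end with study participation | continue on schedule |
| Survival contact | ends with study participation | continues |
| Exception for anaphylaxis | not applicable | none |

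The conflict is real for these four sections. Sections 5.2.4 and Table 5-5 order the drug stopped and are silent on study status, so they are not part of it. They do help with intent: 5.2.5 treats anaphylaxis as an alternative CTCAE category for an infusion reaction and refers to Table 5-5.

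**2. What survives a literal reading?** The close of Section 8 sends all patients, whatever the reason and where possible, to end-of-treatment procedures and the 90-day safety follow-up. Section 8.2 covers patients who withdraw from the study as well as those who stop treatment. Section 8.2.2 mentions tumor or survival assessments within the 90 days. Tables 6-1 and 6-2 mark no imaging at the end-of-treatment or safety visit, so any scan in that period comes from the calendar schedule.

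**3. Which scans fall inside the 90 days?** Inputs: infusions every 3 weeks (Days 1, 22, 43; Section 5.2.1), and scans at Weeks 8 and 16, each ±7 days (Section 6.2.1). The choice of stop days is illustrative.

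- Week 8 window: Day 57 ± 7 = Days 50 to 64.
- Week 16 window: Day 113 ± 7 = Days 106 to 120.

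| Last dose | 90 days later | Week 8 scan | Week 16 scan |
|---|---|---|---|
| Day 1 | 1 + 90 = Day 91 | inside | outside |
| Day 22 | 22 + 90 = Day 112 | inside | partly (Days 106 to 112) |
| Day 43 | 43 + 90 = Day 133 | inside | inside |

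**4. What would the SAP do?** SAP 8.6.4 computes PFS in months as days, counting the first dose as day 1, divided by 30.4375.

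- Week 8 scan done without progression, then no more scans: 50/30.4375 = 1.64 to 64/30.4375 = 2.10 months (nominal 57/30.4375 = 1.87). Death before two consecutive missed assessments would still count as an event.
- No post-baseline scan at all: censored at 1 day, 1/30.4375 = 0.03 months, unless death falls within two assessments of baseline (about 16 weeks).
- DOR uses the PFS censoring rules (SAP 8.6.3).
- OS is censored at the last date known alive (SAP 8.6.5). If that is the 90-day visit, the time is 91/30.4375 = 2.99 to 133/30.4375 = 4.37 months, short of the 12-month landmark. SAP 8.6.5 does not list departure ordered by the protocol among its censoring reasons; applying the same rule is an assumption.

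**5. How many patients?** The documents give no rate for Grade 3 anaphylaxis, and none is assumed. For scale, one patient is 1/15 = 6.7% of an initial naïve combination group or 1/10 = 10% of a pre-treated group of the minimum size (Section 3.1.4).

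**The case against.** The strongest reply is that this is a slip which Section 8 already governs. The protocol uses study loosely for treatment elsewhere, as in Sections 5.3 and 6.2.1. To stop scans, a site would have to prefer one sentence in a section on ancillary treatments over Sections 8.1, 5.6.1 and 3.2. The opening of Section 8 also allows withdrawal from treatment, the study or both for adverse events. Section 8.2 sends even patients who leave the study into follow-up. The endpoints concerned are secondary, and the SAP plans no formal testing.

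Most of this stands, and it limits the severity. It does not remove the inconsistency. The opening of Section 8 is permissive, whereas 5.2.5 is mandatory and 8.1 then requires continued assessments for reason 4. What Section 8.2 and the close of Section 8 clearly secure is the end-of-treatment visit and the 90-day period.

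A reader might go further in three ways that the documents do not support:

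- **That 5.2.4 and Table 5-5 also contradict 5.2.5.** They are silent on study status, and silence is not conflict.
- **That affected patients would typically be censored for PFS at 1 day.** That requires the Week 8 scan to be missed as well, although its window lies inside the 90-day period in all three examples.
- **That the primary endpoint is compromised.** SAP 10.5.2.2 presents ORR for all patients in the FAS, so the patient stays in the denominator. The numerator could change only if a responder lost the confirmatory scan.

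**Conclusion.** Section 5.2.5 is wrong as written, in a minor way. It orders removal from the study where four other sections require continued scans (absent progression) and survival contact. The likely intent is to stop study treatment. This is an internal inconsistency; no design choice is in question.

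The harm depends on a site following the sentence literally and ending contact after the 90-day follow-up. For each such patient, PFS, DOR and OS follow-up would then be cut short for a toxicity-related reason, with PFS censored at about 1.6 to 2.1 months in the illustrated case. The number of patients is probably very small, and the endpoints are secondary and descriptive. Severity is low. The conflict between the sections is certain; any effect on results is conditional.

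**What to change.** Replace the sentence in Section 5.2.5 with wording such as: *After an anaphylactic or anaphylactoid reaction of Grade 3 or higher, study treatment is stopped permanently and the patient is followed up under Sections 8.1 and 8.2.*

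Adding *or higher* covers Grade 4, which 5.2.5 does not mention, and matches Section 5.2.4 and Table 5-5. Section 8 reason 4 allows KY1044 to continue, after discussion with the Medical Monitor, when atezolizumab is stopped for an acute infusion reaction. Whether that option should apply after anaphylaxis is for the sponsor to decide and state.

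The cost is one sentence of protocol text. It needs no new visits or scans, because Sections 8.1, 5.6.1 and 3.2 already require them. The point at which the drug is stopped for an infusion reaction does not move, because Section 5.2.4 and Table 5-5 already stop it above Grade 2.
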